8.1	CLINICAL ADVERSE EVENTS	11
8.2	ADVERSE EVENT REPORTING	11
8	STUDY ADMINISTRATION	11
9.1	TREATMENT ASSIGNMENT METHODS	11
9.2	DATA COLLECTION AND MANAGEMENT	11
9.3	CONFIDENTIALITY	12
9.4	REGULATORY AND ETHICAL CONSIDERATIONS	13
9.4.1	Data and Safety Monitoring Plan	13
9.4.2	Risk Assessment	13
9.4.3	Potential Benefits of Trial Participation	13
9.4.4	Risk-Benefit Assessment	13
9.5	RECRUITMENT STRATEGY	13
9.6	INFORMED CONSENT/ASSENT AND HIPAA AUTHORIZATION	14
9.7	PAYMENT TO SUBJECTS/FAMILIES	14
9.7.1	Reimbursement for travel, parking and meals	14
9.7.2	Payments to parent for time and inconvenience (i.e. compensation)	14
9.7.3	Payments to subject for time, effort and inconvenience (i.e. compensation)	14
9	PUBLICATION	16
10	REFERENCES	17
11	APPENDIX	17
11.1	PROPOSED DEVICE OVERVIEW	19

ABBREVIATIONS AND DEFINITIONS OF TERMS

AE	Adverse event
IDL	Innovative Design Labs
CHOP	Children's Hospital of Philadelphia
IR	Infrared

ABSTRACT

Context:

With the rise in competitive sports participation in pediatric and adolescent populations, there has also been an increase in overuse injuries. Current methods of overuse injury prevention, such as pitch-counting, fail to account for differing techniques or effort and often ignore the elevated risk for children participating in two or more sports emphasizing the same body part. This wearable device seeks to more accurately monitor overuse to prevent and aid rehabilitation of overuse injuries.

Objectives:

The primary objective of this study is to collect motion-capture data on movements common to baseball play in order to develop an algorithm for a wearable device for the prevention and rehabilitation of sports-related overuse injuries. Secondary objectives include evaluating the feasibility of wearing the throwing device during simulated baseball play.

Study Design:

Prospective reliability study.

Setting/Participants:

- Males and female baseball pitchers age 8-14 years old at the time of consent will be included
- Children with an existing injury in their throwing arm will be excluded

Data collection for the Pilot Phase will occur at sports medicine/physical therapy sessions at the Children's Hospital of Philadelphia, including satellite locations. Participants may be approached at the start of their physical therapy sessions at CHOP. Data collection for Phase 1 will occur at the Epic Sports Biomechanics research facility. Participants will be recruited via solicitation from letters sent to local youth sport organizations, fliers placed in the Sports Medicine Centers throughout CHOP, or personal solicitation via email, phone, or in-person contact.

Study Interventions and Measures:

Subjects will be asked to fill out a short survey about their athletic activities. They will wear a prototype of a minimal risk throwing device during simulated baseball play in a sports medicine session or at the Epic Sports Biomechanics research facility. Various motion data from the device and from the Motion Lab analysis will be collected to create and refine an algorithm to quantify workload and throwing movements.

TABLE 1: SCHEDULE OF STUDY PROCEDURES

Study Phase	Screening Pilot Phase	Screening Phase 1	Pilot Phase: Physical Therapy Data Collection	Phase 1: Epic Sports Collection
Visit Number			1	1
Informed Consent/Accent	X	X		
Review Inclusion/Exclusion Criteria	X	X		
Medical Record Review			X	
Athletic History Survey		X	X	
Demographics Survey		X		
Height/Weight			X	X
Physical Examination			X	X
Throwing Exercises with Device			X	X
Epic Sports Biomechanics Evaluation				X

1 BACKGROUND INFORMATION AND RATIONALE

1.1 Introduction

Overuse injuries in youth athletes are commonplace. Current methods of prevention and progressive loading during rehabilitation are rudimentary (e.g. baseball pitch count) and fail to account for the subtleties of differing player technique or effort. A system capable of quantifying biomechanical loads associated with sports movements would substantially aid physicians, therapists, guardians, and coaches in prevention and rehabilitation efforts.

Study team partners at Innovative Design Labs (IDL) in collaboration with Reality Works Inc. have developed a prototype for an advanced wearable device that has potential to track cumulative exposure to injurious forces, monitor adherence to sport-specific overuse standards and rehab regimens, and identify improper throwing technique. The purpose of this study is to collect preliminary and advanced motion data from youth athletes in order to create and refine an algorithm to quantify throwing movements, numbers, and injury associations among youth baseball players for use in this wearable throwing monitor. The Pilot Phase of the study will occur in the CHOP rehabilitation clinic while wearing the prototype device and aims to test and refine rudimentary throwing algorithms using simple throwing and movement tasks. Phase 1 of the study will occur at the Epic Sports Biomechanics research facility and will collect advanced motion-capture data during simulated baseball play in order to improve system hardware, firmware, and algorithms.

1.2 Name and Description of Investigational Product

This sports injury performance monitoring device aims to 1) track exposure to injurious forces 2) monitor adherence to sport specific overuse standards and prescribed rehab regimens, 3) identify improper technique, and 4) meet the practical requirements of a youth-sports monitoring system (e.g. cost, aesthetics, ease-of-use, etc.). An accompanying smart phone application and web interface will be developed as part of the study for use in future product development. More information on the electronic hardware and software can be found in the Appendix, page 20.

As the comfort, ease-of-use, robustness, and appearance of any wearable device is of critical importance to its acceptance, significant effort will be put into analyzing the requirements and testing concepts for the device design in this study phase. Perfecting design and manufacturability will occur in a future study. The sensors will be sealed in soft, hypoallergenic foam to provide resistance to sweat, dirt, and physical impact. Multiple form-factors including arm-bands, elbow compression sleeves, and wrist straps will be investigated, optimizing the combination of easy donning and doffing, maximal comfort, aesthetics, and to accurate motion transfer. The system will include a “zero touch” interface where no user interaction is required to utilize the device. Study team members will be responsible for setting up, powering up, and charging the device. The case will be hermetically sealed creating a dust-tight and waterproof device (IP68 rated).

1.3 Relevant Literature and Data

Youth sports participation in the United States has grown to 46.5 million children annually [1]. Although participation in athletics has numerous health benefits [2], sport-related overuse injuries from excessive stress and/or inadequate recovery periods represent a significant and growing health care concern [3]. Annually, 1.25 million sports-related overuse injuries are reported in emergency rooms with patients 24 years or younger [4] resulting in \$2 billion of healthcare costs [3], [8]–[11]. In addition to cost and pain, these injuries result in lost participation time, numerous physician visits, and lengthy rehabilitation [2]–[5]. Further, athletes with recurrent overuse injuries may stop participating in sports, thus adding to the already increasing numbers of unhealthy sedentary and obese youths [3]. Overuse injuries are preventable through proper monitoring and education; however, adherence to guidelines is often deficient [6]. This device seeks to prevent and aid rehabilitation of such sports-related overuse injuries.

1.4 Compliance Statement

This study will be conducted in full accordance all applicable Children's Hospital of Philadelphia Research Policies and Procedures and all applicable Federal and state laws and regulations including 45 CFR 46 and 21 CFR Parts 50, 56.

The investigators will perform the study in accordance with this protocol, will obtain consent and assent, and will report unanticipated problems involving risks to subjects or others in accordance with The Children's Hospital of Philadelphia IRB Policies and Procedures and all federal requirements. Collection, recording, and reporting of data will be accurate and will ensure the privacy, health, and welfare of research subjects during and after the study.

2 STUDY OBJECTIVES

The overall purpose of the study is to create and refine an algorithm to quantify throwing movements, effort, numbers, and injury associations among youth baseball players for use in a wearable throwing monitor with the hopes of preventing and aiding in the rehabilitation of sports-related overuse injuries.

2.1 Primary Objective (or Aim)

The primary objective of this study is to collect motion-capture data on movements common to baseball play in order to develop a wearable device for the prevention and rehabilitation of sports-related overuse injuries.

2.2 Secondary Objectives (or Aim)

The secondary objectives are to:

- Develop algorithms to quantify injury associated with common baseball injuries
- Evaluate the feasibility of wearing the throwing monitor during a simulated baseball game

- Validate simplistic device measurements (Pilot Phase)

3 INVESTIGATIONAL PLAN

3.1 General Schema of Study Design

This study will occur in two phases with two different subject groups. The Pilot Phase will include 10 evaluable subjects and occur in the sports medicine physical therapy clinic at the Children's Hospital of Philadelphia. Subjects will be asked to perform simple throwing movements as part of or in addition to their rehabilitation regimen. This will test the ability of the prototype device to detect basic movements.

Phase 1 will include 10 evaluable subjects and occur at the Epic Sports Biomechanics research facility. Subjects will partake in a simulated baseball game while wearing the prototype device and additional baseball-related movements while being tracked by the Epic Sports Biomechanics research facility's infrared sensors. The goal of this phase is to create and refine a more robust algorithm for the device that can track various throwing movements and track potential injurious forces or poor techniques.

This study is a prospective reliability study.

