3.1.2 Pilot Phase Cohort: Physical Therapy Throwing Session

During the Pilot Phase, subjects that have been identified, consented, and enrolled will wear a prototype of IDL's throwing monitor device during the duration of their physical therapy appointment. Subjects will wear the device somewhere on their arm and may or may not be asked to perform throwing movements as part of their rehabilitation regimen. This phase will test if the device is able to detect basic throwing movements and create an accurate pitch count.

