3.2 Study Duration, Enrollment and Number of Sites

3.2.1 Duration of Study Participation

The study duration per subject will be 1 day for screening, and 1 day for throwing evaluation for both the Pilot and Phase 1 groups.

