4.2 Study Treatment Phase

4.2.1 Pilot Phase Study Visit

- Informed consent and assent

Subjects will be asked to put on the throwing monitor device prototype at the beginning of their physical therapy session and will wear the device for the duration of the visit or until asked by a member of the study team to remove the device. Subjects will be asked to do the following tasks while wearing the device:

- Complete any physical therapy rehabilitation exercises given by their physical therapist as part of their care
- Complete a limited number of additional throwing exercises within in the limits of the rehabilitation regimen
- Complete athletic history survey (not required to wear device for survey completion)
- Medical record review
- Height and weight measurements if not collected as part of clinical care
- Physical exam if not collected as part of clinical care
- Return throwing device at end of session or earlier if requested by study team

No subject will be asked to complete any motions or tasks that may hinder their rehabilitation regimen.

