4.2.2 Phase 1 Study Visit

At the Epic Sports Biomechanics research facility, subjects will be asked to do the following activities:

- Height and weight measurements
- Physical Exam
- Wear the prototype device and participate in a simulated game
 - Pitch approximately 30-45 times using varying pitch types (fastball, change-up, etc.)
- Complete additional baseball-related movements with full the Epic Sports Biomechanics research facility monitors in a random order, including
 - Field-based overhand throws
 - Runs

- Bat swings
- Catching balls
- Return throwing device at end of session or earlier if requested by study team

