5.1.6 Phase 1 Throwing Evaluations

At the Epic Sports Biomechanics research facility, subjects will wear the throwing monitor device prototype during a simulated baseball game, pitching approximately 30-45 times using varying pitch types (fastball, change-up, etc.) as they would within a typical game. In addition, each player will perform a set of other baseball-specific movements (field-based overhand throw, run, bat swing, catch ball) typically seen in baseball play. Participants will be fitted with 51 infrared reflective markers to enable tracking of limb, torso, and head movement while actions are performed. Movement data will be video recorded and recorded with 12 Motion Analysis Raptor IR cameras encompassing a capture volume of 26ft length x 7ft width x 8ft height. A minimum of 3 time-synchronized video cameras placed at different viewing perspectives will also record participants as they perform movements. Subjects will be asked to return the throwing monitor device by the end of the study visit.

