6.3 Statistical Methods

6.3.1 Baseline Data

Data will be analyzed with the goal of determining the feasibility of the approach. The accuracy of movement classification, movement phase segmentation, mapping of sensor reading to biomechanical values, and movement detection will all be quantified. K-fold cross validation will be used to estimate the performance of regressors and classifiers. Regressor performance will be quantified via the mean and standard deviation of error values between predicted biomechanical variable values and actual values as determined from motion capture data. Biomechanical value prediction models will be considered successful if error distributions have mean and standard deviation of less than 5% and 10% respectively of the nominal value. Sensitivity and specificity will be used to quantify the

performance of movement detection and classification algorithms. Movement segment detection will be considered correct if the algorithm identifies 90% of time occupied by the movement. Detection algorithms will be considered successful if they are able to operate with specificity and sensitivity of 95%.

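### The reliability label is not supported by the planned design or analysis, and the Section 6.3.1 success rule does not separate between-athlete bias from pitch-to-pitch error

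*Combined protocol and SAP*

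**What the plan says.** The abstract gives the design as "Prospective reliability study", and Section 3.1 repeats it: "This study is a prospective reliability study".

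On the number of sessions, Section 3.2.1 says: "The study duration per subject will be 1 day for screening, and 1 day for throwing evaluation for both the Pilot and Phase 1 groups". Table 1 likewise shows one visit per phase, and Section 3.1 says that the two phases use different children.

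The objectives (2.1, 2.2) and endpoints (6.1, 6.2) cover motion data, algorithm development, injury-related quantification, feasibility of wear and validation of basic device measurements. None mentions reliability.

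Section 6.3.1 uses K-fold cross-validation, with sensitivity and specificity for detection and classification. For the biomechanical predictions, "Regressor performance will be quantified via the mean and standard deviation of error values between predicted biomechanical variable values and actual values", the latter taken from motion capture. A prediction model succeeds if its error mean is under 5% and its error SD under 10% of nominal.

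Sections 3.1.3, 4.2.2 and 5.1.6 give about 30-45 pitches of mixed types per Phase 1 child. The Pilot Phase sets no number. Its children "may or may not be asked to perform throwing movements as part of their rehabilitation regimen" (3.1.2), and the extra task in 4.2.1 is to "Complete a limited number of additional throwing exercises within in the limits of the rehabilitation regimen".

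**The concern.** Reliability concerns whether a measurement repeats, across throws, across refittings of the device or across days. Agreement with a reference is accuracy, a different property. A protocol that names the first and analyses only the second invites a reader to credit the device with something that was not examined.

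The distinction has a practical side. Section 1.1 presents the device as a way to track cumulative exposure, and the cost functions in Section 5.2.1 score accumulated overuse risk. Over many pitches, random pitch-to-pitch error largely cancels. An error that belongs to the athlete does not. Such error is plausible here: ages run from 8 to 14, several form factors are under investigation (1.2), and in the Pilot Phase the position on the arm is left open (3.1.2). A success rule based on an error mean and SD, with no split by athlete, cannot show which kind of error dominates.

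**Working it through.** **The plan's own figures.** No stated figure bears on reliability. Enrolment reproduces: 20 enrolled for 10 evaluable in each phase implies 50% loss, 10 / (1 - 0.5) = 20, and 2 x 20 = 40, as in Section 6.4. The only numerical limits that matter here are the 5% and 10% in 6.3.1.

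**Label against content.** A between-session or re-donning comparison needs at least two fittings per child. The plan has one session and describes no refitting, so that kind of reliability cannot be estimated. Within-session repeatability needs repeated throws and a within-child statistic. Phase 1 has repeated throws, but no such statistic is planned: the documents name no intraclass correlation, repeatability coefficient or within-subject SD.

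**What the 10% SD limit can hide.** Let B be the between-athlete SD of error and W the within-athlete SD, both in percent of nominal. The total SD is sqrt(B^2 + W^2). The error SD of a child's mean over k pitches is sqrt(B^2 + W^2/k), assuming independent pitch-to-pitch errors. The documents give no variance components, so the splits below are assumptions, each with a total SD of 10%.

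| B / W | k = 30 | k = 45 |
|---|---|---|
| 3 / 9.54 | sqrt(9 + 91/30) = 3.47 | sqrt(9 + 91/45) = 3.32 |
| 7.07 / 7.07 | sqrt(50 + 50/30) = 7.19 | sqrt(50 + 50/45) = 7.15 |
| 9.54 / 3 | sqrt(91 + 9/30) = 9.56 | sqrt(91 + 9/45) = 9.55 |

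The extreme rows differ by a factor of 9.56/3.47 = 2.8 at 30 pitches and 9.55/3.32 = 2.9 at 45. All three rows have the same total SD and get the same verdict under 6.3.1.

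**What Phase 1 could estimate.** Suppose the game pitches carry a motion-capture reference. Ten children then give 10 x 29 = 290 to 10 x 44 = 440 within-child degrees of freedom. The 95% chi-square limits for W are 0.925-1.089 times the estimate at 30 pitches and 0.938-1.071 at 45. If only 10-15 pitches per child were of one type (an assumption), there would be 90-140 degrees of freedom and limits of 0.87-1.17 to 0.90-1.13.

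For B there are 9 degrees of freedom, and the chi-square factors are 0.688 and 1.826. These apply to the SD of the observed child means, which still contains W^2/k. In the 3 / 9.54 case at 30 pitches, W^2/k = 3.03 and the variance of a child mean is 9 + 3.03 = 12.03. With W^2/k treated as known:

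- lower limit: sqrt(12.03 x 0.688^2 - 3.03) / 3 = 0.54
- upper limit: sqrt(12.03 x 1.826^2 - 3.03) / 3 = 2.03

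So about 0.69-1.83 is the best case for B, reached when within-child noise is negligible.

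**Whether the reference exists for game pitches.** Section 3.1.3 puts the game first and mentions the infrared markers with the movements that follow. Section 4.2.2 ties the facility's monitoring to the additional movements. Section 5.1.6 describes the game, the other movements and then the markers and cameras, without limiting them to either. Section 6.3.2 gives pitches as an example for video review, which does not settle it. If only the additional movements are referenced, the 290-440 degrees of freedom do not apply, because no repetition count is given for those movements.

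**The case against.** The strongest reply is that reliability is only a design label. No objective, endpoint, decision rule or sample size depends on it. Section 6.3.1 sets feasibility as the goal, 6.4 calls the study exploratory, and the accuracy analysis fits the stated objectives. On this view a wording edit in two places is enough. That holds for the label. It does not answer the second part: the success thresholds are the plan's own, and they ignore the error component that matters most for a cumulative measure. Being exploratory explains the missing power calculation and nothing more.

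Other objections limit what can be claimed, and they stand:

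- A reader might infer that every child supplies 30-45 repeated pitches. Only the 10 evaluable Phase 1 children do. Those pitches are of mixed types, so they are not pure replicates, and they may lack a reference.
- A reader might infer that 6.3.1 prescribes one pooled SD over all throws. It does not say so. It speaks of error distributions and leaves the unit of summary open.
- Section 6.3.1 does not say how the folds are formed. If a child's throws fall in both training and test sets, athlete-specific bias can be partly learned and B understated. A random-athlete model alone would then give false reassurance.
- The variance splits are illustrative and are not estimates for this device.

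**Conclusion.** The point holds in limited form. As planned, the study assesses accuracy and does not support its reliability label, and its success rule does not distinguish athlete-level bias from pitch-to-pitch error. The possible consequence is an almost threefold difference in the error of a child's mean load (about 3.3-3.5% against 9.6%) under one verdict. This assumes a total SD at the 10% limit, independent pitch errors and the two extreme splits shown.

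A reader might go further and conclude that the study could say nothing about repeatability. The documents do not support that. One session rules out test-retest and re-donning reliability, but within-session repeatability in Phase 1 may be obtainable and is simply not planned. Nor is the sample size invalidated, since it makes no power or precision claim. The matter deserves correction but does not threaten the study's stated objectives.

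**What to change.** 1. **Abstract and Section 3.1.** Replace the label with: algorithm-development and accuracy study. State that test-retest and re-donning reliability are not assessed.
2. **Section 6.3.1, Phase 1 only.** Split the cross-validation folds by child. Fit a model with a random athlete effect, and movement or pitch type as a fixed effect, to the held-out per-throw device-minus-motion-capture errors. Using errors against the reference keeps true variation between pitches from being counted as device error. Report the between-athlete and within-athlete SDs with confidence intervals, beside the overall error mean and SD.
3. **Sections 3.1.3, 4.2.2 and 5.1.6.** Reconcile them on whether game pitches carry a motion-capture reference. If they do, apply the model to the pitches. If not, apply it to the repeated referenced movements and state how many there are per child.

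The cost is wording and slightly more analysis, with no extra visit or child. The between-athlete SD will be wide with 10 children and may look less favourable than the overall SD. The report should say so.
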